ICH	International Conference on Harmonization
IEC	Independent Ethics Committee
IGF-1	insulin-like growth factor-1
IGFBP3	insulin-like growth factor binding protein 3
IgM	immunoglobulin M
INR	international normalized ratio
IRB	Institutional Review Board
ISIS 766720	antisense inhibitor of GHR
MB	major bleeding
MCH	mean corpuscular hemoglobin
MCHC	mean corpuscular hemoglobin concentration
MCV	mean corpuscular volume
MRI	magnetic resonance imaging
mRNA	messenger ribonucleic acid
NCS	not clinically significant
NOAEL	no-observed-adverse-effect-level
NSAID	non-steroidal anti-inflammatory drug
NYHA	New York Heart Association
on study	The patient is 'on study' from signing of the informed consent until their last study visit
OGTT	oral glucose tolerance test
PD	pharmacodynamic(s)
PE	physical examination
pH	measure of the acidity or basicity of a solution
PK	pharmacokinetic(s)
PPS	per protocol set
PT	prothrombin time
PTWk5	Post-Treatment Week 5
QoL	quality of life
RNA	ribonucleic acid
RNase H1	an ubiquitous endonuclease that specifically hydrolyzes the RNA strand in RNA/DNA hybrids
SAE	serious adverse event
SF36	36-item Short Form Survey
siRNA	small interfering ribonucleic acid
SC	subcutaneous(ly)
Study Day 1	defined as the first day ISIS 766720 product is administered to the patient
Study Drug	ISIS 766720

SRL	somatostatin receptor ligands
SUSAR	suspected unexpected serious adverse reaction
TEAE	treatment-emergent adverse event
T _{max}	time to maximal concentration
ULN	upper limit of normal
UPCR	urine protein/creatinine ratio
WBC	white blood cell
WOCBP	women of childbearing potential

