3.4.3. Post-Treatment

Patients are to return to the Study Center for follow-up visits for 14 weeks after last injection of ISIS 766720 per Schedule of Procedures in [Appendix A](#). Any patient who receives at least 1 dose of ISIS 766720 will be required to complete the Post-Treatment Period. The final study visit will be 14 weeks after the last injection (PTWk15).

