6.1.2. Treatment Period

During the 1.5-year study, each patient will receive up to 20 SC doses of ISIS 766720 with a planned monthly interval between each dose except for a booster dose at Day 15 (WK 3). All patients will have bi-weekly visits beginning at Day 1 (WK 1) through Day 113 (WK 17). After that visits occur monthly through Day 505 (WK 73) with an additional visit on Day 183 (WK 27) for primary endpoint assessments. Of the 24 required study visits, 14 selected study visits may be performed outside of the clinic by a Sponsor selected Home Health Care professional (See [Appendix A](#)). Home health visits are optional and would be arranged by study center staff if requested by the patient. In consultation with the Sponsor, a Home Health Care visit may be conducted for a study visit day that was intended to be an in-clinic visit. It is preferable that the entire visit is conducted, however the following assessments may be omitted: ECG, body weight, physical exam, ring size, and OGTT. If a visit cannot be performed in the clinic or by Home Health, patient contact (e.g., phone, text, email or video) is required by site personnel to assess any adverse events or changes in concomitant medications. Any assessments not completed at the Home Health Care visit should be attempted at the next clinic visit.

Safety, efficacy, PK and exploratory assessments will be performed per [Appendix A](#), [Appendix B](#), and [Appendix C](#) throughout the Treatment Period on ISIS 766720 administration days. At each visit, patients should arrive fasting at least 8 hours for safety and clinical laboratory evaluations; vital signs, blood pressure (BP) assessments, AEs and concomitant medication usage will be assessed during each visit.

A 2-hour OGTT and GH response procedure will be conducted pre-dose on Day 1 and pre-dose on Day 183 (WK 27) and Day 505 (WK 73). The pre-dose-Day 1 OGTT and GH response procedure may be conducted between Day -41 and pre-dose Day 1. To decrease the study burden on potential patients, it is suggested that this procedure is done after the patient has completed and qualified based on all other screening procedures. The OGTT and GH Response procedure can be conducted in the clinic or as arranged by a Home Health Care professional. The patient must fast 10-hours prior to OGTT and GH Response assessment.

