Quality of life assessments and general health assessments including ASTS-M, AcroQOL, EQ5-D, and SF-36 questionnaires will be assessed along with ring size assessment periodically throughout the study. See Section [6.2.3](#) for a description of the study procedures. Study required procedures at study visits are listed in the Schedule of Procedures in [Appendix A](#), [Appendix B](#), and [Appendix C](#). Patient will be requested to complete AcroQoL, ASTS-M, EQ5-D, and SF-36 and ring size assessments prior to all other procedures and dosing (see Section [6.2](#)).

All blood samples should be drawn prior to ISIS 766720 administration (exceptions are the post-dose samples for PK sampling at Day 1 and Day 113).

An MRI (3×) and Echocardiogram (2×) will be done. See [Appendix A](#) for timing of procedure.

During each visit, the study staff should attempt to complete all the study procedures prior to ISIS 766720 administration as outlined in the [Appendix A](#), however, if a procedure is conducted after ISIS 766720 administration it will be considered a deviation that does not impact the evaluation of efficacy.

All safety data including AEs and concomitant medications will be reviewed by the Sponsor's Medical Monitor or Designee on an ongoing basis throughout the trial. Early termination patients from the Treatment Period will be requested to enter the 14-week Post-Treatment Period. The first visit to complete is an "early termination from treatment" visit entitled ETTX. The ETTX visit should be completed as soon as possible after the decision is made, preferably 4 weeks after the last dose. The remainder of the Post-Treatment visits should then follow the schedule which are in intervals relative to the patients last dose ([Appendix A](#)). All patients receiving at least 1 dose of study medication are required to enter the Post-Treatment Period for continuing safety evaluations. Please contact your CRA at the time of early termination to review the schedule.

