8.5. Safety Monitoring Rules

Please refer also to the 'Guidance for Investigator' section of the Investigator's Brochure.

For the purposes of safety monitoring Baseline is defined as:

- Monitoring Rules for Liver Chemistry Tests, Renal parameters, and Platelets – Unless otherwise specified, baseline is defined as the average of pre-dose values

In addition to the standard monitoring of clinical safety parameters, the following guidelines are provided for the monitoring of selected parameters chosen based on preclinical and clinical observations for ISIS 766720 as well as other ASOs.

Confirmation Guidance: At any time during the study (Treatment or Post-Treatment Periods), the initial clinical laboratory results meeting the safety monitoring criteria presented below **must be confirmed** by performing measurements (ideally in the same laboratory that performed the initial measurement) on new specimens. All new specimen collections should take place as soon as possible (ideally within 7 days of the initial collection). For stopping rules, if the initial laboratory result is observed during the Treatment Period, the results from the re-test **must be available** prior to administering the next dose of ISIS 766720.

Re-dosing Guidance: Patients with initial laboratory test values that reach a stopping rule must not be re-dosed until the re-test results are available. In general, patients who do not meet the

stopping rules based upon re-test may continue dosing. However, the Investigator and the Sponsor Medical Monitor (or appropriately qualified Designee) should confer as to whether additional close monitoring of the patient is appropriate. If any of the stopping criteria described in Section 8.6 are met, the patient will be permanently discontinued from further treatment with ISIS 766720, evaluated fully as outlined below and in consultation with the Sponsor Medical Monitor (or appropriately qualified Designee), and will be followed up in accordance with Section 8.8 of the Protocol.

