8.6.3. Stopping Rule for Platelet Count Results

In the event of any platelet count less than $50,000/\text{mm}^3$, dosing of the patient with ISIS 766720 will be stopped permanently. Platelet count will be monitored at least twice weekly until 3 successive values $> 75,000/\text{mm}^3$ then weekly until 3 values $> 100,000/\text{mm}^3$ ([Table 4](#)).

Administration of steroids is recommended for patients whose platelet count is less than $25,000/\text{mm}^3$. Treatment guidelines for immune thrombocytopenia ([Provan et al. 2010](#)) recommend Dexamethasone 40 mg daily for 4 days every 2-4 weeks for 1-4 cycles; Prednis(ol)one 0.5-2 mg/kg/d for 2-4 weeks then taper; or methylprednisolone 30 mg/kg/day for 7 days.

Note: Patient may require continuation with oral steroids after methylprednisolone treatment is stopped.

In the event of a platelet count $< 75,000/\text{mm}^3$ and $> 50,000/\text{mm}^3$, and in the absence of MB or clinically relevant non-major bleeding (CRNMB) (defined below; ([Schulman and Kearon 2005](#); [Buller et al. 2007](#)) , dosing with ISIS 766720 should be suspended temporarily until the platelet count has recovered to $> 100,000/\text{mm}^3$. The suitability of the patient for continued dosing will be determined by the Investigator in consultation with the Sponsor Medical Monitor or Designee and will be based on factors such as the original rate of decline in the patient's platelet count, whether any bleeding events were experienced, and the speed of recovery of platelet count after interruption of dosing. If dosing is reinitiated, platelet count must be measured weekly until the end-of-study.

If, after reintroduction of ISIS 766720, the platelet count falls below $75,000/\text{mm}^3$, further dosing of the patient with ISIS 766720 will be stopped permanently.

Definition of Major Bleeding Events ([Schulman and Kearon 2005](#)):

1. Fatal bleeding, and/or
2. Symptomatic bleeding in a critical area or organ, such as intracranial, intraspinal, intraocular, retroperitoneal, intraarterial or pericardial, or intramuscular with compartment syndrome
3. Clinically overt bleeding leading to transfusion of ≥ 2 units of packed red blood cells or whole blood or a fall in hemoglobin of 2.0 mg/dL (1.24 mmol/L) or more within 24 hours

Definition of Clinically Relevant Non-Major Bleeding Events ([Buller et al. 2007](#)):

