Clinically relevant CRNMB is defined as overt bleeding not meeting the criteria for MB but that resulted, for example, in medical examination, intervention, or had clinical consequences for a patient.

Definition of Minor Bleeding Events:

Minor bleeding events are those that do not fulfill the criteria for MB or CRNMB (defined above).

Table 4: Actions in Patients with Low Platelet Count

Platelet Count	Drug Dose	Monitoring
> 100,000/mm ³	No action	Monitor per Schedule of Procedures every 2 weeks (+7 days) up to Week 17 and every 4 weeks (+7 days) after Week 17
≥ 75,000 to ≤ 100,000/mm ³	No action	Monitor every week until 3 successive values > 100,000/mm ³
≥ 50,000 to < 75,000/mm ³	Pause dosing When platelet count returns to > 100,000/mm ³ restart dosing only if approved by Sponsor Medical Monitor or Designee	Monitor at least twice weekly until 3 successive values > 75,000/mm ³ then weekly until 3 values > 100,000/mm ³ . If redosing then continue to monitor weekly for the remainder of the Treatment Period. If not redosing then subsequent monitoring should be per the Schedule of Procedures. Consider discontinuation of antiplatelet agents/non-steroidal anti-inflammatory drug (NSAIDS)/anticoagulant medication while platelet count < 75,000/mm ³ .
≥ 25,000 to < 50,000/mm ³	Permanently discontinue ISIS 766720	Monitor twice weekly until 3 successive values > 75,000/mm ³ then weekly until 3 values > 100,000/mm ³ . Subsequent monitoring should be per the Schedule of Procedures. Discontinue antiplatelet agents/NSAIDS/anticoagulant medication while platelet count < 75,000/mm ³ if possible.
< 25,000/mm ³	Permanently discontinue ISIS 766720	Monitor daily until 3 successive values show improvement then monitor twice weekly until 3 successive values > 75,000/mm ³ then weekly until 3 values > 100,000/mm ³ . Subsequent monitoring should be per the Schedule of Procedures. Steroids recommended* Consider need for hospitalization and referral to hematologist Discontinue antiplatelet agents/ NSAIDS/ anticoagulant medication while platelet count < 75,000/mm ³ if possible

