Appendix A. Schedule of Procedures – Post-Treatment Period

Study Period	Post-Treatment Period (14 Weeks)			ETTX ^{1, 2}	ETPT ^{1, 2}
Study Week (Wk) from Last Dose	PTWk5	PTWk9	PTWk15	ETTX ^{1, 2}	ETPT ^{1, 2}
Study Day from Last Dose	PTD29 ²	PTD57 ²	PTD99 ²	NA	NA
Study Day from Day 1	533	561	604	NA	NA
Visit Window ±	7	7	7	NA	NA
Home Health Care Visit Option ³	X	X			
MRI/CT of sellar				X ¹³	
Echocardiogram				X ¹⁴	
AcroQoL			X	X	X
ASTS-M			X	X	X
EQ-5D			X	X	X
SF-36			X	X	X
Ring Size Measurement			X	X	X
Body Weight			X	X	X
Vital Signs ⁴	X	X	X	X	X
Physical Exam ⁵			X	X	X
ECG (12-Lead)			X	X	X
Adverse Events	X	X	X	X	X
Concomitant Medications	X	X	X	X	X
Pregnancy Test ⁶	X	X	X	X	X
Chemistry Panel (Fasting) ^{7, 8}	X	X	X	X	X
Hematology ⁸	X	X	X	X	X
Partial PD Panel: GH, IGF-1, GHBP ⁷	X	X			
Full PD Panel ⁷			X	X	X

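### Section 8.6.3 runs weekly platelet counts after re-dosing to end-of-study, but its Table 4 stops them with the Treatment Period and omits the permanent stop after a second fall

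*Combined protocol and SAP*

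**What the plan says.** Protocol Section 8.5.2 sends any platelet count below 75,000/mm³ to Section 8.6.3, which has a text part and an action table (Table 4).

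**Weekly counts after re-dosing.** The text says "If dosing is reinitiated, platelet count must be measured weekly until the end-of-study". Table 4, in the row for 50,000 to <75,000/mm³, says "If redosing then continue to monitor weekly for the remainder of the Treatment Period".

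**Second fall after reintroduction.** The text stops dosing permanently if the count drops below 75,000/mm³ once the drug has been reintroduced. The dose cell of the same row gives only a pause, then a restart above 100,000/mm³ with Medical Monitor approval. It has no entry for a patient who has already been re-challenged.

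**How the protocol uses the word study.** End-of-study is not defined.
- The glossary says a patient is on study "from signing of the informed consent until their last study visit".
- Section 3.4.3 says "The final study visit will be 14 weeks after the last injection" and names that visit PTWk15.
- The confirmation guidance in Section 8.5 opens with "At any time during the study (Treatment or Post-Treatment Periods", so there the study covers both periods.
- Section 6.1.2 is looser. It begins "During the 1.5-year study" when describing the dosing period, and it counts 24 required study visits.

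**The concern.** Text and table belong to the same section, apply to the same patient, and give different end points for weekly counts. A site working from the table would drop to the ordinary post-treatment schedule after the last dose. The patients concerned have already had a platelet fall and then been re-exposed. Section 6.1.2 says that all dosed patients are "required to enter the Post-Treatment Period for continuing safety evaluations", so this period is meant for safety follow-up.

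The missing permanent stop matters for a related reason. The table is laid out as the list of actions by platelet band, and its two lowest bands do state permanent discontinuation. A reader could take the 50,000 to <75,000/mm³ row as complete and ask for a second restart that the text forbids.

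**Working it through.** The plan states no figure to reproduce. The check sets the two rules side by side and counts post-treatment platelet tests under each.

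**1. Do the two end points differ?** Section 3.4 lists a 73-week Treatment Period and, separately, a 14-week Post-Treatment Evaluation Period. If end-of-study is the last study visit, the text runs to PTWk15 and the table stops 14 weeks earlier. If end-of-study meant the end of dosing, the two rules would agree and every difference below would be 0. The glossary, Section 3.4.3 and Section 8.5 favour PTWk15. Against it, Section 6.1.2 uses the word study for the dosing period, and its 24 required visits match the 24 Treatment Period visits in Appendix A (Week 1 to Week 73).

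**2. Inputs.**
- Last dose: Day 505, which is dose 20 of up to 20 (Section 6.1.2, Appendix A).
- Scheduled post-treatment hematology: PTWk5, PTWk9 and PTWk15, listed as Days 533, 561 and 604 from Day 1, or PTD29, PTD57 and PTD99 from the last dose (Appendix A).
- Visit window: ±7 days (Appendix A).

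**3. Number of counts after the last dose.**
- Text: one per week for 14 weeks, on Days 512, 519, 526, 533, 540, 547, 554, 561, 568, 575, 582, 589, 596 and 603. That is 98 / 7 = 14.
- Table: the 3 scheduled draws.
- Difference: 14 − 3 = 11 at most.

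**4. Longest gap between post-treatment counts.**
- Text: 7 days.
- Table, from the PTD numbers: 99 − 57 = 42 days.
- Table, from the Day 1 numbers: 604 − 561 = 43 days.
- Table, with PTWk9 taken 7 days early and PTWk15 taken 7 days late: 43 + 7 + 7 = 57 days.

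**5. What would narrow the gap.** Under Section 8.5.2 and Table 4, a count of 100,000/mm³ or less triggers weekly or closer monitoring. The figures therefore hold only while counts stay above that level. Section 3.4 also allows extra visits for abnormal results, at a frequency the Medical Monitor sets with the investigator. The figures assume none are ordered.

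**6. Permanent stop.** The rule is in the Section 8.6.3 text. Section 8.8 requires discontinuation when any stopping rule in 8.6.1 to 8.6.3 is met, and the re-dosing guidance in Section 8.5 says the same of the Section 8.6 criteria. Only the table row is silent.

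**The case against.** The strongest reply has four parts.

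- **End-of-study is undefined**, and Section 6.1.2 shows that study can mean the dosing period. This stands as a limit on certainty. PTWk15 remains the more natural reading, and a mandatory test with an unclear stop date needs correcting in any case.
- **The gap is a worst case.** Every re-dosed patient is already known to the Medical Monitor, who can order extra visits under Section 3.4. This stands. The 42 to 57 days describe the schedule as written, not what must happen.
- **The permanent stop is not in doubt.** A reader might infer that the table permits a second restart against the text. The documents do not support that: three sections require the stop, and the row itself makes restart depend on sponsor approval. This part of the point is an omission only.
- **Few patients are involved.** The trial plans about 40 patients, only re-challenged ones are concerned, and no rate of platelet falls is given. This stands, so the number affected cannot be estimated.

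Two further readings are tempting and fail. First, the text limits temporary suspension to patients without major or clinically relevant non-major bleeding, and the row drops that condition. A reader might infer that bleeding patients in this band have no stated action. They do, because the row's instruction to pause carries no bleeding condition and so covers them. Second, the text asks for consultation with the Medical Monitor before restart and the table asks for approval. These are compatible, approval being the stricter form.

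**Conclusion.** The inconsistency on weekly counts is real and lies in current text. On the natural reading of end-of-study, a re-dosed patient treated to Day 505 would have at most 11 fewer post-treatment platelet counts under the table than under the text, and a longest scheduled gap of 42 to 43 days (57 at the window limits) instead of 7. This rests on three assumptions: end-of-study is PTWk15, counts stay above 100,000/mm³, and no additional visits are ordered. The missing permanent stop in the same row is a lesser matter of completeness.

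The point concerns the safety monitoring of a small, unquantified group. It does not touch the sample size, the primary analysis or any efficacy endpoint. It is worth correcting because the change is cheap and the patients concerned are those already shown to be susceptible.

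**What to change.** Edit the 50,000 to <75,000/mm³ row of Table 4:

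- (a) End weekly counts after re-dosing at end-of-study (PTWk15) instead of at the end of the Treatment Period. Naming the visit also settles the undefined term.
- (b) Add that ISIS 766720 is permanently discontinued if the count falls below 75,000/mm³ after reintroduction. Leave the row's existing twice-weekly then weekly monitoring in place.

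Do not carry the text's no-bleeding condition into the row. That would remove the pause that now covers bleeding patients in this band.

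The cost is an edit to one table row. If end-of-study is PTWk15, no counts are added beyond those the text and table together already require.

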8.7. Adjustment of Dose and/or Treatment Schedule

ISIS 766720 dose adjustments and interruptions will be allowed for safety, tolerability or efficacy. Dose adjustments for efficacy (no higher than a 200 mg dose) may be made after Week 17 IGF-1 results are available. It is recommended to maintain an adjusted dose for efficacy for 3 months prior to further adjustment. Any dose adjustment requires consultation with the Sponsor Medical Monitor or Designee.

Patients may have their dose interrupted in response to AEs after consultation with Sponsor Medical Monitor or Designee.

8.8. Discontinuation of Study Drug/Treatment

A patient must permanently discontinue study treatment for any of the following:

- The patient becomes pregnant. Report the pregnancy according to instructions in Section [9.4](#)
- The patient withdraws consent
- The patient experiences an AE that necessitates permanent discontinuation of ISIS 766720
- The patient develops laboratory test abnormalities that meet any of the stopping rules listed in Sections [8.6.1](#) to [8.6.3](#)
- The patient meets any of the following Exclusion Criteria (see Section [5.2](#)) after discussion with the Sponsor Medical Monitor (or appropriately qualified Designee)
 - Patient needing pituitary surgery or radiation during Treatment Period
 - Patient with a pituitary tumor that is worsening (e.g., either growing, or at risk of compressing or abutting the optic chiasm or other vital structures) as assessed by pituitary/sellar MRI protocol
 - Treatment with any other acromegaly medications

The reason for discontinuation of ISIS 766720 must be recorded in the electronic Case Report Form (eCRF) and source documentation.

Patients who discontinue ISIS 766720 should complete early termination from treatment visit (ETTX) and then enter the Post-Treatment Period) unless consent is withdrawn. Minimally, every effort should be made to complete the ETTX (see [Appendix A](#), Section [6.1.2](#)).

If the patient declines or is unable to participate in the above, the Investigator should clarify what type of follow-up the patient is agreeable to: in person, by phone/mail, through family/friends, via correspondence/communication with other physicians, and/or from review of the medical records. Wherever possible, these patients should continue to be followed up via the agreed means to collect information on AEs, concomitant medications and survival status. At the very least, the patient's status at the end of the protocol defined study period should be ascertained and documented wherever possible. The agreed means of follow-up will be documented in the patient records and the Sponsor notified.

